6.6 Post Treatment assessments (Appendix 4)

1. Outpatient visits will occur at weeks 196, 200, 204, 208, 212, 216, 228, and 240 for participants in both treatment groups.
2. Laboratory testing (liver panel) plus telephone assessment can replace an outpatient visit at weeks 208 and 212 if ALT at the preceding assessment (week 204 and week 208, respectively) is <300 U/L for men or <200 U/L for women and bilirubin is normal (total bilirubin <1.5 mg/dL or direct bilirubin <0.5 mg/dL)

3. Medical history and physical exam at week 240.
4. Clinical evaluation at weeks 196, 200, 204, 208, 212, 216, and 228.
5. Assessment of adverse events and concomitant medications at each visit.
6. Questionnaires (quality of life, depression assessment, fatigue, and health behaviors) at week 240.
7. Symptom questionnaire at each visit.
8. CBC including platelets, alkaline phosphatase, albumin, total protein, and creatinine at week 240.
9. Renal panel (creatinine, calculated creatinine clearance, phosphate, blood urea nitrogen, and calcium) at each study visit for participants who are on Tenofovir
10. Hepatic panel (ALT, AST, albumin, total protein, alkaline phosphatase, total and direct bilirubin) at each visit.
11. Urinalysis at week 240.
12. PT/INR at weeks 196, 200, 204, 216, and 240.
13. Blood samples for serum/plasma at each outpatient visit.
14. Qualitative HBsAg, HBeAg, and anti-HBe at weeks 216 and 240.
15. Anti-HBs and antiviral drug resistance testing at week 240.
16. HBsAg quantification at weeks 204, 216, 228, and 240.
17. HBeAg quantification at weeks 204, 216, 228, and 240.
18. HBV DNA at each outpatient visit
19. Ultrasound exam (If clinically indicated, per AASLD guidelines, done as standard of care) at week 240.
20. Fibroscan (if available and obtained at, or since, the week 180 visit but not later than the week 192 visit) at week 240.

6.7 Assessment of adherence

At each study visit, study personnel will review the study drug dosing schedule with participants and counseling on adherence will be provided. At each study visit while on therapy, participants will be asked to return all bottles of tenofovir and used vials of peginterferon alfa-2a to document how much study medications were used. Serum drug levels may be measured on stored serum samples.

6.8. Management of non-response

Definition: Primary non-response is defined as a failure to achieve a $>1\text{-log}_{10}$ IU/mL decline in HBV DNA after the first 24 weeks of treatment. HBV DNA will be measured by the quantitative HBV DNA assay which will be reconfirmed with re-testing 4 weeks later (week 28). Compliance with study medications will be assessed and documented. Primary non-response is considered to be treatment failure.

Management of non-response

- 6.9.1.** Reinforce compliance when non-response is initially suspected.
- 6.9.2.** Testing of Tenofovir DF levels may be performed (samples will be archived for analysis and not available in real-time).
- 6.9.3.** If serum HBV DNA report confirms that participant meets criteria for virological non-response, change to combination emtricitabine/tenofovir within 2 weeks of obtaining the week 28 result.
- 6.9.4.** Participants will be assessed at weeks 4, 8 and 12 and then every 12 weeks after initiation of rescue therapy to document the response. Thereafter, participants will be followed per protocol.

6.9.5. If serum HBV DNA is ≥ 1000 IU/mL by HBV DNA quantitation assay after 24 weeks of rescue therapy, subsequent treatment will be altered at the discretion of the study physician.

6.10 Management of a partial virological response

Definition: A partial virological response is defined as a decrease of serum HBV DNA $> 1 \log_{10}$ IU/mL by week 24 but a level $\geq 100,000$ IU/mL confirmed on two consecutive visits (weeks 36 and 48). A partial virological response is considered to be treatment failure.

6.10.1. Reinforce compliance when partial response is initially suspected.

6.10.2. Testing of Tenofovir DF levels may be performed (samples will be archived for analysis).

6.10.3. If serum HBV DNA report confirms participant meets criteria for partial virologic response, change to combination emtricitabine/tenofovir within 2 weeks of obtaining the week 48 result

6.10.4. Participants will be assessed at weeks 4, 8 and 12 weeks and then every 12 weeks after initiation of rescue therapy to document the response. Thereafter, participants will be followed per protocol.

6.10.5. If serum HBV DNA is ≥ 1000 IU/mL by HBV DNA quantitation assay by week 24 of rescue therapy, subsequent treatment will be altered at the discretion of the study physician.

6.11. Management of virological breakthrough

Definition: Virological breakthrough is defined as a $> 1 \log_{10}$ IU/mL increase in HBV DNA level from nadir or redetection of serum HBV DNA after disappearance that is confirmed on re-testing 4 weeks later in a participant verified to be medication compliant. If the re-test confirms virological breakthrough, a blood sample will be tested for genotypic resistance.

6.11.1. Reinforce compliance when virological breakthrough is initially suspected. The importance of compliance with study medication will be reinforced with study participants at each visit.

6.11.2. Testing of Tenofovir DF levels may be performed (samples will be archived for analysis).

6.11.3. Resistance mutations will be evaluated by sequencing stored samples.

6.11.4. Selection of rescue therapy will be based upon the cross-resistance profile of the mutation(s) present when available. If unavailable, emtricitabine/tenofovir will be used. Rescue therapy should be started within 4 weeks of confirming the virological breakthrough. The time to start of rescue therapy may be adjusted depending upon the time required for resistance testing to be completed.

6.11.5. Participants will be assessed at weeks 4, 8 and 12 weeks and then every 12 weeks after initiation of rescue therapy to document the response. Thereafter, participants will be followed per protocol.

6.11.6. If serum HBV DNA is ≥ 1000 IU/mL by week 24 of rescue therapy, treatment will be changed at the discretion of a study physician.

6.12 Definition and management of on-treatment hepatitis flares

On-treatment hepatitis flare is defined as increase in ALT to ≥ 300 U/L for men and ≥ 200 U/L for women AND > 3 times baseline (day 0) value. Participants who meet criteria of a flare will be seen every 4 weeks until ALT decreases to < 300 U/L for men and < 200 U/L for women. Severe on-treatment hepatitis flare is defined as ALT ≥ 1000 U/L regardless

of gender. Participants who meet criteria of a severe flare will be seen every week until ALT decreases to <1000 U/L, at which point they will be evaluated every 4 weeks until ALT <300 U/L for men and <200 U/L for women and thereafter at scheduled visits per study protocol. Participants who experience hepatitis flares may continue treatment if total bilirubin is <2.0 mg/dL and direct bilirubin <1.0 mg/dL. Participants who experience severe hepatitis flares may continue treatment at the discretion of the investigator if total bilirubin is <2.0 mg/dL and direct bilirubin <1.0 mg/dL.

6.13. End-of-treatment (prior to week 192) assessment

6.13.1. Eligibility criteria for discontinuation of treatment prior to week 192

Participants who meet either of the criteria below will be discontinued from treatment:

- Grade IV toxicity (laboratory or clinical)
- Hepatic decompensation while on peginterferon defined by:
 - Total bilirubin ≥2.0 mg/dL and direct bilirubin ≥1.0 mg/dL
 - Any clinical decompensation
- Participant refuses to continue treatment/participation in study

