5.1. Dosage and administration

Participants will be randomly assigned to receive one of the following treatments during the treatment period of the study:

- Treatment A: Tenofovir DF 300 mg by mouth once daily for 192 weeks.
- Treatment B: Peginterferon alfa-2a 180 µg by subcutaneous injection once weekly in combination with tenofovir DF 300 mg by mouth once daily for 24 weeks followed by tenofovir DF 300 mg once daily for 168 weeks (192 weeks total therapy).

All participants will be instructed to take one tablet of tenofovir DF once daily without regards to meals. Participants in treatment arm B will also be instructed to take 180 µg of peginterferon alfa-2a subcutaneously once weekly. Participants in treatment arm B will be instructed to inject the peginterferon alfa-2a on the same day each week.

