6.13.2. End of treatment assessment

Participants who stop treatment early will complete assessments specified for the week 192 visit (see section 6.5 and Appendix 3).

Participants who discontinue treatment due to Grade IV toxicity or hepatic decompensation will continue to be followed until these events are resolved or stabilized, according to the post-treatment follow-up schedule.

6.13.3. Follow-up visit schedule after week 192

All participants who are eligible to stop treatment at week 192 will be seen at weeks 196, 200, 204, 208, 212, 216, 228, and 240 (corresponding to weeks 4, 8, 12, 16, 20, 24, 36, and 48 post-treatment for those whose treatment is discontinued). This is the minimal follow up required. Laboratory testing (liver panel) plus telephone assessment can replace an outpatient visit at weeks 208 and 212 if ALT at the preceding assessment (week 204 and week 208, respectively) is <300 U/L for men or <200 U/L for women and bilirubin is normal (total bilirubin <1.5 mg/dL or direct bilirubin <0.5 mg/dL). Additional visits for safety monitoring should be included as needed. Participants who are not eligible to stop treatment at week 192 and who remain on treatment will be seen at weeks 204, 216, 228 and 240 (i.e., 12, 24, 36 and 48 weeks after week 192).

Laboratory testing will be performed as outlined in Appendix 4. Blood samples for serum/plasma will be collected at each outpatient visit.

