6.14.2. Criteria for treatment reinitiation in the Post-Treatment Follow up Period

Tenofovir DF will be restarted for any one of the following:

- Any one of the three criteria: INR ≥ 1.3 , total bilirubin ≥ 3.0 mg/dL or direct bilirubin ≥ 1.0 mg/dL, regardless of HBV DNA or ALT level.
- Any clinical decompensation, regardless of HBV DNA or ALT level.
- HBV DNA $\geq 10,000$ IU/mL and ALT > 1000 U/L (male or female) (i.e. only one ALT value > 1000 U/L is needed to qualify).
- HBV DNA $\geq 10,000$ IU/mL and ALT ≥ 300 U/L for males, ≥ 200 U/L for females. A total of one HBV DNA $\geq 10,000$ IU/mL and any three ALT values ≥ 300 U/L (male) or ≥ 200 U/L (female) over the 4-week (or longer) time frame are needed to qualify. Treatment will be resumed if the third ALT remains ≥ 300 U/L (male) or ≥ 200 U/L (female).
- HBV DNA $\geq 10,000$ IU/mL and ALT ≥ 150 U/L for males or ≥ 100 U/L for females. A total of one HBV DNA $\geq 10,000$ IU/mL and any three ALT values ≥ 150 U/L (male) or ≥ 100 U/L (female) over the 12 week (or longer) time period are needed to qualify. Treatment will be resumed if the third ALT remains ≥ 150 U/L (male) or ≥ 100 U/L (female).
- HBsAg-positive and HBeAg-positive at week 192.
- HBsAg-positive, HBeAg-negative, and anti-HBe-negative at week 192

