6.14.3. Management after reinitiation of treatment

Participants who meet criteria for treatment reinitiation specified in section 6.14.2 will be restarted on Tenofovir DF 300mg daily. Tenofovir DF will be provided by the study until week 240. Monitoring of AST, ALT and HBV DNA levels will be done at 4, 8 and 12 weeks after Tenofovir DF is restarted and then every 12 weeks. If bilirubin or INR is abnormal at the time of treatment reinitiation, it (they) should be monitored at 4, 8, and 12 weeks after Tenofovir DF is restarted and then every 12 weeks until it (they) return(s) to normal. If, after treatment reinitiation, the participant meets criteria for non-response (section 6.9) or partial response (section 6.10), the drug therapy will be changed as outlined in those sections.

7. Adverse events and toxicity management

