7.1. Criteria for permanent and premature discontinuation of treatment

- Death
- Grade IV toxicity (laboratory or clinical)
- Hepatic decompensation defined by:
 - Total bilirubin ≥ 2.0 mg/dL and direct bilirubin ≥ 1.0 mg/dL
 - Any clinical decompensation

7.2.a. Adverse effects of peginterferon alfa-2a

Common side effects of peginterferon alfa-2a include influenza-like symptoms, particularly with the first few injections, fatigue, neuropsychiatric symptoms such as depression and reduction in white blood cell counts and platelet counts. Hyper- or hypothyroidism has been noted to occur in up to 5% of participants receiving peginterferon alfa-2a.

Some rare but potentially serious side effects include:

- neuropsychiatric complications, which may include suicide, suicidal ideation, acute psychosis and severe depression
- serious and severe bacterial infections; fatal infections have been reported during treatment with peginterferon alfa-2a
- pancreatitis
- interstitial pneumonitis, fatal cases have been reported with peginterferon alfa 2a use

Other possible but uncommon adverse events associated with peginterferon alfa-2a include:

- development or exacerbation of existing autoimmune disorders such as rheumatoid arthritis, systemic lupus erythematosus, idiopathic thrombocytopenic purpura, hemolytic anemia, type 1 diabetes, psoriasis, etc.
- pulmonary disorders including dyspnea, pulmonary infiltrates, and sarcoidosis
- exacerbations of inflammatory bowel disease
- eye disorders, including decrease or loss of vision, retinal hemorrhages
- hearing disorders, including loss of hearing and tinnitus
- hypersensitivity reactions including severe skin reactions, in the spectrum of Stevens Johnson syndrome

7.2.b. Peginterferon alfa-2a dose reductions

Factors that will lead to a reduction in the dose of peginterferon alfa-2a include:

1. Disabling symptoms, which, in the opinion of the study physician, are related to peginterferon alfa-2a treatment and prevent the participant from performing his/her occupation or daily tasks.
2. A rash consistent with allergic reaction or vasculitis.
3. Reductions in the neutrophil count according to the guidelines in Appendix 2.
4. A reduction in platelet count according to the guidelines in Appendix 2.
5. Any adverse reaction, which, in the opinion of the study physician, places the participant at increased risk of a serious adverse effect.

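### Section 7.1 makes the hepatic-decompensation stop permanent with no limit by arm, drug or period, while 6.13.1 limits the same stop to peginterferon; read literally, 7.1 withdraws tenofovir DF from a decompensating participant

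*Combined protocol and SAP*

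**What the plan says.** Section 6.13.1 lists reasons for ending treatment before week 192. One is "Hepatic decompensation while on peginterferon defined by" total bilirubin of at least 2.0 mg/dL with direct bilirubin of at least 1.0 mg/dL, or by any clinical decompensation. Section 7.1 is headed "Criteria for permanent and premature discontinuation of treatment". Its bullet reads "Hepatic decompensation defined by" and then gives the same two branches, with no mention of peginterferon. Both sections speak of treatment without saying which drug.

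Under section 5.1, arm A takes tenofovir DF alone for 192 weeks. Arm B takes peginterferon with tenofovir DF for 24 weeks and then tenofovir DF alone for 168 weeks.

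Section 6.13.2 says that participants who stop for Grade IV toxicity or "hepatic decompensation will continue to be followed until these events are resolved or stabilized, according to the post-treatment follow-up schedule". For the post-treatment period, 6.14.2 says "Tenofovir DF will be restarted for any one of the following", and one of the listed criteria is "Any clinical decompensation, regardless of HBV DNA or ALT level". Section 6.14.3 adds that "Tenofovir DF will be provided by the study until week 240".

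**The concern.** A site with a decompensating participant on tenofovir DF alone finds two answers. Section 7.1 orders a permanent stop; the hepatic bullet of 6.13.1 orders none. If the site follows 7.1, the drug withdrawn is the only antiviral the participant is taking. Section 7.3.a itself warns that hepatitis can worsen when anti-HBV agents are stopped, so the literal instruction is unsafe at the point where the participant is most vulnerable. The event is foreseeable: cirrhosis is a stratification factor, and section 7.6.1 lists hepatic decompensation among the disease-related outcomes. What is at stake is participant safety and uniform conduct across sites, not the error rate or power.

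**Working it through.** No figure in the plan depends on this point, so the check sets the rules side by side.

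| Section | Trigger | Who and when | Action |
|---|---|---|---|
| 6.13.1 | total bilirubin ≥2.0 and direct ≥1.0 mg/dL, or any clinical decompensation | only while on peginterferon | treatment stopped, drug not named |
| 7.1 | same | no limit by arm, drug or period | permanent stop, drug not named |
| 6.5.1, week 192 | clinical decompensation, or direct bilirubin >0.5 mg/dL | participants still on treatment | not eligible to stop; tenofovir DF continues to week 240 or end of study |
| 6.12, flares | total bilirubin <2.0 and direct <1.0 mg/dL | any participant with an on-treatment flare | treatment may continue, drug not named |
| 6.14.2 | INR ≥1.3, or total bilirubin ≥3.0, or direct ≥1.0 mg/dL, or any clinical decompensation | post-treatment follow-up | tenofovir DF restarted |

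1. **Arm A throughout, and arm B after week 24.** The hepatic bullet of 6.13.1 cannot apply, because nobody is on peginterferon. The 7.1 bullet does apply, and by section 5.1 the only planned drug it can stop is tenofovir DF.

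2. **Arm B, weeks 0 to 24.** The two triggers coincide. Only 7.1 calls the stop permanent, and neither section says whether tenofovir DF stops with peginterferon. Sections 7.2.c and 7.2.d do say so for intolerance and depression: peginterferon stops and tenofovir DF continues.

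3. **Approach to week 192.** Section 6.5.1 uses the week-180 results and anything found up to the week-192 visit. A participant found to be decompensated in that window must continue tenofovir DF under 6.5.1 and must stop it permanently under 7.1.

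4. **Overlap with the restart rule.** The 7.1 laboratory branch needs direct bilirubin ≥1.0 mg/dL, and that alone meets a 6.14.2 criterion. A grid over total bilirubin 0 to 9.9 mg/dL in steps of 0.1, with direct no higher than total, gives 0 cases that meet 7.1 and miss 6.14.2. The clinical branch is the same in both. So every 7.1 event meets a restart criterion while it persists. The reverse does not hold: total 1.0 with direct 1.0 mg/dL, or INR ≥1.3 alone, meets 6.14.2 but not 7.1.

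5. **Does 6.14.2 reach early stoppers?** Section 6.13.2 puts them on the post-treatment schedule, and Appendix 4 covers those who stop early for an adverse event. Section 6.14.2 makes no exception for a permanent stop. No text says which of the two prevails.

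**The case against.** **The restart rule serves another purpose.** Section 6.14 concerns relapse after stopping, two of the 6.14.2 bullets are tied to week 192, and 6.4.1 has the resumption criteria reviewed at week 180 with participants due to stop. Appendix 4 is a chart of visits and tests, not a treatment rule. Decompensation on therapy and decompensation after withdrawal can reasonably call for different actions. This stands. A reader might infer that 7.1 and 6.14.2 flatly contradict each other; the documents support only an ambiguity.

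**Section 7.1 is not alone in reaching tenofovir-only time.** A reader might infer that 7.1 is the only stopping rule relevant to decompensation there. That is not so. Section 6.12 uses the same bilirubin cut-offs for flares in both arms, and the Grade IV stop in 6.13.1 is unrestricted. This also stands, so the share of planned treatment time outside the peginterferon period does not measure the size of the problem.

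**The broad scope may have been intended.** Section 6.12 gives some support to that reading, and the documents do not settle it. Against it, 5.3.3 calls peginterferon contraindicated in decompensated cirrhosis, which explains a stop specific to that drug, and 6.5.1 keeps decompensated participants on tenofovir DF.

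**Rescue is available.** Section 5.6 allows other anti-HBV drugs if medically indicated during the study, and follow-up continues until the event resolves or stabilises. Section 7.3.b recommends an alternative anti-HBV drug immediately, but under its renal and phosphate headings and for participants discontinued from the study. These provisions soften the harm. They do not tell a site what to do after a 7.1 stop for decompensation.

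**Conclusion.** The mismatch between 6.13.1 and 7.1 is plain on the text, and for participants on tenofovir DF alone the literal effect of 7.1 is an unsafe instruction. It should be corrected. The conclusion assumes that the missing qualifier in 7.1 means what it says: both arms, at any time before the planned end of treatment.

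The likely number affected is small, given the entry criteria, but it cannot be estimated from the documents. Actual harm would be limited where sites use the restart rule or prescribe another antiviral. The sample size (188 per arm, 376 in total) and the intention-to-treat primary analysis are untouched.

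**What to change.** Make three wording changes:

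- In 7.1, limit the decompensation bullet to the time on peginterferon, as 6.13.1 does.
- In both 6.13.1 and 7.1, state that peginterferon is permanently stopped while tenofovir DF, or other anti-HBV therapy, continues, subject to the renal and phosphate stopping rules in 7.3.b and 7.3.d.
- In 6.12, state that the bilirubin ceiling for continuing treatment through a flare governs peginterferon, not tenofovir DF.

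Since the documents do not settle the intended scope, the sponsor should confirm it when making the edit. The sponsor should also say how the Grade IV bullet applies to a decompensation graded IV, because that bullet names no drug either. The cost is a few lines of text, with no new data, visits or analyses.

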6.13.2. End of treatment assessment

Participants who stop treatment early will complete assessments specified for the week 192 visit (see section 6.5 and Appendix 3).

Participants who discontinue treatment due to Grade IV toxicity or hepatic decompensation will continue to be followed until these events are resolved or stabilized, according to the post-treatment follow-up schedule.

6.13.3. Follow-up visit schedule after week 192

All participants who are eligible to stop treatment at week 192 will be seen at weeks 196, 200, 204, 208, 212, 216, 228, and 240 (corresponding to weeks 4, 8, 12, 16, 20, 24, 36, and 48 post-treatment for those whose treatment is discontinued). This is the minimal follow up required. Laboratory testing (liver panel) plus telephone assessment can replace an outpatient visit at weeks 208 and 212 if ALT at the preceding assessment (week 204 and week 208, respectively) is <300 U/L for men or <200 U/L for women and bilirubin is normal (total bilirubin <1.5 mg/dL or direct bilirubin <0.5 mg/dL). Additional visits for safety monitoring should be included as needed. Participants who are not eligible to stop treatment at week 192 and who remain on treatment will be seen at weeks 204, 216, 228 and 240 (i.e., 12, 24, 36 and 48 weeks after week 192).

Laboratory testing will be performed as outlined in Appendix 4. Blood samples for serum/plasma will be collected at each outpatient visit.

6.14. Assessment and management of relapse after stopping therapy

6.14.1. Definition of relapse

Virological relapse: Persistent HBV DNA ≥1000 IU/mL during the follow-up period (on at least two samples at least 12 weeks apart, with one of them being more than 24 weeks after stopping therapy) in HBeAg-positive or HBeAg-negative participants.

Biochemical relapse will be defined as an elevated ALT (>30 U/L for females and >45 U/L for males if normal at end of treatment or an increase of 1.5 X end of treatment level if abnormal at end of treatment) on at least two samples at least 12 weeks apart, with one of them being at least 24 weeks after stopping therapy.

An ALT flare will be defined as an ALT level ≥ 300 U/L for males or ≥ 200 U/L for females.

These definitions will be used for data analyses, see section 6.14.2 for criteria to reinitiate treatment.

Monitoring of participants

- Participants with an increase in total bilirubin to ≥ 3 mg/dL or direct bilirubin to ≥ 1 mg/dL or INR ≥ 1.3 (regardless of ALT and HBV DNA levels) must be reassessed as soon as possible and within 1 week for liver panel, PT/INR, CBC, and creatinine. The laboratory testing should continue every week until INR < 1.3 and either total bilirubin < 3 mg/dL or direct bilirubin < 1 mg/dL.
- Participants with an ALT > 1000 U/L for both males and females (regardless of HBV DNA levels) must be reassessed as soon as possible and within 1 week. Thereafter, weekly monitoring of liver panel, bilirubin (total or direct), PT/INR, HBV DNA should continue until ALT ≤ 1000 U/L.
- Participants with an ALT ≥ 300 U/L for males or ≥ 200 U/L for females (regardless of HBV DNA levels) must be reassessed within 1 week and thereafter, every 2 weeks for liver panel, HBV DNA, bilirubin (total or direct), and PT/INR. The laboratory testing should continue until ALT < 300 U/L for males or < 200 U/L for females.
- Participants with an ALT ≥ 150 U/L for males or ≥ 100 U/L for females (regardless of HBV DNA levels) must be reassessed within 4 weeks and thereafter every 4 (± 1) weeks for liver panel, HBV DNA, bilirubin (total or direct), and PT/INR. The laboratory testing should continue until ALT < 150 U/L for males or < 100 U/L for females.

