Thus, the advantages of nucleos(t)ide analogue therapy are the ease of administration, the lack of significant side effects and the consistent suppression of HBV DNA that can be achieved, particularly with the newer agents such as tenofovir DF and entecavir. While emergence of drug resistance can limit the efficacy of oral agents, a low rate of antiviral resistance (1% or less even with prolonged therapy for 4 to 5 years), is seen with entecavir and tenofovir DF, reflective of their greater potency and higher genetic barrier to resistance. As a consequence 80-90% of patients treated long-term with these agents achieve rates of marked suppression of HBV DNA levels and normal ALT levels. The advantage of peginterferon therapy is that it is administered for a limited period (6 to 12 months) and results in loss of HBsAg in a significant proportion of patients. Previous studies have shown that a one-year course of combination therapy of peginterferon and nucleos(t)ide analogue does not yield a higher response rate than a one-year course of either agent alone (21). However, these studies have been limited by the use of a nucleos(t)ide analogue with high risk of resistance (e.g. lamivudine) and a relatively short course of treatment. Thus, an obvious question is whether the combination of a limited course of peginterferon (6 or 12 months) with long-term therapy with a potent nucleos(t)ide analogue (tenofovir DF or entecavir for at least 4 years) will provide a higher rate of loss of HBsAg and ability to stop therapy without relapse. This clinical trial compares the efficacy of peginterferon plus a potent nucleotide analogue, tenofovir DF, for 24 weeks followed by monotherapy with tenofovir DF for a further 3.5 years to the efficacy of that same potent nucleotide analogue, tenofovir DF, given for a full 4 years. The primary measure of outcome will be HBsAg loss in serum 240 weeks after starting antiviral therapy.

2. Study objectives

To define the role of limited duration peginterferon alfa-2a in the presence of tenofovir for treating people with chronic hepatitis B by:

- Evaluating “off treatment” sustained responses following combination therapy consisting of peginterferon alfa-2a plus tenofovir DF versus tenofovir DF monotherapy.
- Comparing the on-treatment efficacy of initial treatment with combination therapy consisting of peginterferon alfa-2a plus tenofovir DF versus tenofovir DF monotherapy.

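### The section 6.14.1 relapse definitions can miss participants who restart tenofovir early and are re-suppressed before the required late sample

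*Combined protocol and SAP*

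**What the plan says.** Section 6.14.1 gives three definitions for the period after stopping.

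- Virological relapse: HBV DNA at or above 1000 IU/mL "on at least two samples at least 12 weeks apart, with one of them being more than 24 weeks after stopping therapy".
- Biochemical relapse: raised ALT "on at least two samples at least 12 weeks apart, with one of them being at least 24 weeks after stopping therapy". A sample at exactly week 24 can therefore serve for biochemical but not for virological relapse.
- ALT flare: "An ALT flare will be defined as an ALT level" at or above 300 U/L (males) or 200 U/L (females), with no timing rule and no second sample.

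The section then states: "These definitions will be used for data analyses, see section 6.14.2 for criteria to reinitiate treatment".

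Section 6.14.2 says "Tenofovir DF will be restarted for any one of the following" and sets no minimum time off drug. Three criteria combine HBV DNA at or above 10,000 IU/mL with ALT:

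- ALT above 1000 U/L ("i.e. only one ALT value > 1000 U/L is needed to qualify");
- three values at or above 300/200 U/L over at least 4 weeks;
- three values at or above 150/100 U/L over at least 12 weeks.

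The others are raised INR or bilirubin, "Any clinical decompensation, regardless of HBV DNA or ALT level", and two week-192 serology patterns.

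Section 6.14.3 then measures ALT and HBV DNA 4, 8 and 12 weeks after restart and every 12 weeks thereafter. No section counts a restart as relapse, censors at restart, or says whether samples taken back on drug may be used.

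**The concern.** The persistence rule suits a participant who stays off drug. For one who is re-treated, persistence off drug can no longer be observed, yet the rule taken literally scores it as absent. Because the fastest restarts go with the highest ALT, the miss is not random: an early, severe, promptly treated relapse is more easily lost than a mild, late one.

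The Background asks whether the combination "will provide a higher rate of loss of HBsAg and ability to stop therapy without relapse". A relapse rate built on these definitions would bear on the second half of that question, and it would be too low by an amount that depends on how early and how hard participants relapse.

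**Working it through.** **The plan's own figure.** The documents state none for relapse. The sample size (141 per arm for 5% vs 15%, and 282/(1 - 0.25) = 376 in total) reproduces, but it concerns HBsAg loss and does not bear on this point.

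**Inputs.** Post-treatment visits fall at weeks 4, 8, 12, 16, 20, 24, 36 and 48 (section 6.13.3), with scheduled HBV DNA at 4, 8, 12, 24, 36 and 48 (Appendix 4). Samples after restart follow section 6.14.3. Time from restart to control is not given, so 4, 8, 12 and 24 weeks are assumed.

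**Step 1: earliest restart.** Take the first abnormal result at week 4 and add the minimum qualifying time.

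- ALT above 1000: 4 + 0 = week 4
- ALT at or above 300/200: 4 + 4 = about week 8
- ALT at or above 150/100: 4 + 12 = about week 16

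All three precede the required late sample.

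**Step 2: one participant.** HBV DNA is 1,000,000 IU/mL and ALT 1200 U/L at week 8, with restart that week. Section 6.14.3 gives samples at 8 + 4 = 12, 8 + 8 = 16, 8 + 12 = 20, then 32 and 44. The first HBV DNA sample later than week 24 is at week 32, after 32 - 8 = 24 weeks on drug. The first ALT sample that can serve for biochemical relapse is at week 24, after 24 - 8 = 16 weeks on drug. If ALT is controlled by week 24 and HBV DNA by week 32, and both stay controlled, neither definition is met.

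**Step 3: all tiers.** Onset was set at weeks 4, 8, 12, 16, 20 and 24, with HBV DNA and ALT turning abnormal at the same visit and controlled at the same time. Both definitions were then tested on the available samples. Entries are the onset weeks missed.

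| Restart criterion | Control 4 wk | Control 8 wk | Control 12 wk | Control 24 wk |
|---|---|---|---|---|
| One ALT >1000 | both: 4-24 | both: 4-24 | both: 4-24 | virological only: 4-12 |
| Three ALT ≥300/200 | both: 4-24 | both: 4-24 | both: 4-8; virological only: 12 | virological only: 4-8 |
| Three ALT ≥150/100 | both: 4-8; virological only: 12 | both: 4; virological only: 8 | virological only: 4 | none |

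Misses increase with the speed of restart and of control.

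**Step 4: the spacing rule also contributes.** With onset and immediate restart at week 24 and control at 12 weeks, the abnormal HBV DNA samples are at weeks 24, 28 and 32. Two of them are late enough, but the widest gap is 32 - 24 = 8 weeks, short of 12.

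**Step 5: sensitivity to simultaneous onset.** If HBV DNA rises before ALT, some later-onset entries become counted. With HBV DNA at or above 1000 from week 12, restart at week 20 and control at 20 + 12 = week 32, the week-28 sample is abnormal and 28 - 12 = 16 weeks after the first, so virological relapse is met. The week-8 example is unchanged.

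**Step 6: illustrative size, by assumption only.** If 10-30% of true relapsers are missed, a true 40% is reported as 40 × 0.90 = 36% down to 40 × 0.70 = 28%.

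**The case against.** The strongest reply is that little depends on these definitions. The primary endpoint is HBsAg loss at week 240, relapse is not listed in sections 2.2.1 to 2.2.9, and section 8 specifies no comparison of relapse between arms. That stands. A reader might infer from the Background that the trial's main question is compromised; the documents do not support this, because the same Background paragraph names HBsAg loss as the primary measure.

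Second, the ALT flare definition has no timing rule and is also designated for analysis. Anyone restarted under the ALT >1000 or ≥300/200 criteria is recorded there. That stands too, so it would be wrong to say that the severest cases vanish from the data. They are recorded as flares and not as relapses. Restarts under the ≥150/100 criterion need not reach the flare threshold.

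Third, a reader might infer that re-treated relapsers are generally scored as not relapsed. That is too strong. The restart criteria apply throughout follow-up, samples taken back on drug can satisfy the definitions, and with control at 24 weeks biochemical relapse is met in every tier.

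Fourth, a reader might infer that a difference between arms is erased or reversed. An erasure can be constructed. If 20% of stoppers in one arm and 5% in the other restart early and are all missed, and 25% in each relapse later, then 45% vs 30% is reported as 25% vs 25%. Those inputs are chosen to produce a tie. Nothing in the documents suggests that the arms differ in this way, and the example shows no reversal.

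The persistence requirement itself is a reasonable guard against transient rises. It fails only where treatment has removed the chance to observe persistence.

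**Conclusion.** The gap is real and narrow. Read literally, the analysis definitions in section 6.14.1 can classify a participant who relapsed early, restarted tenofovir under section 6.14.2 and was re-suppressed as having neither virological nor biochemical relapse. The tendency grows with the speed of restart, and both the 24-week requirement and the 12-week spacing contribute.

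The consequence is confined to the relapse analyses. Its size cannot be stated, because it depends on how many participants restart, when they restart and how fast they are controlled. That stoppers had held HBV DNA below 1000 IU/mL for 24 weeks on treatment (section 6.5.1) makes re-suppression plausible but gives no time to control. The definitional finding is firm; every percentage above is an assumption. It should be corrected because a definition designated for analysis should measure what it names, and the correction is cheap.

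**What to change.** Change the analysis text only and leave every restart criterion in section 6.14.2 as it is. In section 6.14.1, with a matching sentence in section 8:

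1. For analysis, count a restart under any of the three HBV DNA/ALT criteria as virological and biochemical relapse, dated at restart.
2. Report restarts made only for INR, bilirubin, clinical decompensation or week-192 serology as one separate, mutually exclusive category, whatever the HBV DNA level, so that nobody is counted twice.
3. Do not use samples taken after restart as evidence of no relapse.
4. Keep the two-sample persistence rule for participants who are not re-treated.
5. Report relapse with and without the restart-defined events.

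The cost is a few sentences; HBV DNA and ALT are already collected in follow-up and after restart. The reported relapse rate will rise somewhat, and some restarts without 12 weeks of observed persistence will be counted. Item 5 shows how much of the result depends on that choice.
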